4.4.3.3. Vital Signs

Vital signs data will be summarized based on observed values by treatment sequence and visit, as well as change from baseline by treatment sequence and visit. Change from baseline will be calculated using one baseline for both periods (Day 1). A listing of all Vital signs data and a listing of PCI Vital signs data will be produced.

Vital signs data includes the following variables:

- Heart rate
- Blood pressure (SBP, DBP)

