2. SCHEDULE OF ACTIVITIES (SOA)

Procedure	Screening ¹		Treatment Period ²					Follow-up ¹
	Week -4	Week -2	Day 1	Day 15	Day 29 ³	Day 43	Day 57	Day 70
Informed Consent	X							
Entry Criteria	X ⁴	X ⁴	X ⁴					
Physical, Medical History, Demography, Height	X ^{5,9}	X ^{5,9}	X ^{5,9}					
Weight	X		X	X		X		
HemoCue Hgb	X	X	X	X	X	X	X	
eGFR	X							
Females: Urine Pregnancy Test ⁶	X		X		X		X	X
Females: Estradiol & FSH ⁷		X						
HIV screening and Hepcidin	X							
Randomization			X					
Administration of isotopic iron				X		X		
Blood sampling for isotopic iron					X	X	X	
Crossover ⁸					X			
ECG		X						X
Vital signs	X		X		X		X	X
Clinical chemistry & hematology ¹⁰	X							X
Urinalysis ¹⁰	X							X
Liver chemistry monitoring ¹¹				X		X		
Folate & Vitamin B ₁₂		X						
hsCRP		X						
Ferritin and TSAT		X						
Iron status markers ¹²			X	X	X	X	X	
Indices of erythropoiesis ¹³			X	X	X	X	X	
Blood draw for PGx			X					
AE and SAE Assessment ¹⁴	X ¹⁵	X ¹⁵	X	X	X	X	X	X
Review Concomitant Medications	X	X	X	X	X	X	X	X

- ¹ Allowable time window \pm 3 days.
- ² Allowable time window \pm 2 days.
- ³ All assessments to be performed **PRIOR** to crossing over.
- ⁴ Criteria to be assessed can be found in Section 9.4.1.
- ⁵ Complete physical examination, medical history & demography to be performed at Week -4, while a brief physical examination to be performed at Week -2 and Day 1.
- ⁶ Local urine testing will be standard for the protocol unless serum testing is required by local regulation or IRB/IEC.
- ⁷ As detailed in Inclusion Criteria.
- ⁸ Participants that had been administered daprodustat during treatment Period 1 will be switched to rhEPO, while those on rhEPO will be switched to daprodustat. Examples on switching are provided in the Study Reference Manual (SRM).
- ⁹ Height is only collected at Week -4.
- ¹⁰ Clinical laboratory assessments guidance can be found in Section 9.4.5
- ¹¹ Liver chemistry monitoring guidance can be found in Section 9.4.6.
- ¹² Iron status markers include serum iron, ferritin, transferrin, transferrin saturation (TSAT), soluble transferrin receptor, hepcidin and erythroferrone and are described in Section 9.8.2. All samples for iron status markers to be taken pre dose.
- ¹³ Indices of erythropoiesis include Hgb, hematocrit, red blood cell number, mean corpuscular volume, reticulocyte Hgb and reticulocyte number and are described in Section 9.8.3.
- ¹⁴ Guidance on the timing and need for collection of AEs & SAEs are described in Section 9.2.

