1.1. Objectives, Estimands and Endpoints

Since the primary endpoint analyses are based on the Evaluable Population, subjects with intercurrent events who discontinue treatment in either period will be excluded from the primary analysis. Missing data post withdrawal will not be imputed.

Objectives	Endpoints
Primary	

 Compare the efficacy of daprodustat to rhEPO (i.e., epoetin alfa or darbepoetin alfa) on iron absorption 	
 Difference in fractional oral iron absorption (%) between daprodustat and rhEPO
Secondary	

 Characterize the effect of daprodustat or rhEPO on markers of iron status Characterize the effect of daprodustat or rhEPO on indices of erythropoiesis 	
 Change from baseline (Day 1) at 14 and 28 days following treatment with daprodustat or rhEPO in serum iron, transferrin, transferrin saturation, soluble transferrin receptor, ferritin, hepcidin and erythroferrone Change from baseline (Day 1) at 14 and 28 days following treatment with daprodustat or rhEPO in Hgb, hematocrit, red blood cell number, mean corpuscular volume, reticulocyte Hgb and reticulocyte number

Objectives	Endpoints
Safety	

 • Assess safety and tolerability 	
 • Incidence and severity of adverse events and serious adverse events • Reasons for discontinuation of study medication 
Vital signs assessments

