4.4.1. Extent of Exposure

- Number of days of exposure to study drug will be calculated based on the formula:
Duration of Exposure in Days = Treatment Stop Date – (Treatment Start Date) + 1
- Duration will be summarized by treatment group. Each subject will contribute duration of exposure to the treatment taken.
- Participants who were randomized but did not report a treatment start date will be categorised as having zero days of exposure.

A listing and summary table of exposure will be created.

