4.4.2. Adverse Events

Adverse events analyses including the analysis of adverse events (AEs), Serious AEs (SAEs) and other significant AEs will be based on GSK Core Data Standards. An overview summary of AEs, including counts and percentages of participants with any AE, AEs related to study intervention, SAEs related to study intervention, fatal SAEs, and fatal SAEs related to study intervention will be produced. Adverse events will be coded using the standard Medical Dictionary for Regulatory Affairs (MedDRA dictionary). A summary of number and percentage of participants with any adverse events by maximum severity will be produced. A separate summary will be provided for

study intervention-related AEs. A study intervention-related AE is defined as an AE for which the investigator classifies the possible relationship to study intervention as “Yes”. A worst-case scenario approach will be taken to handle missing relatedness data, i.e. the summary table will include events with the relationship to study intervention as ‘Yes’ or missing. The summary table will be displayed by PT only. All SAEs will be tabulated based on the number and percentage of participants who experienced the event. Separate summaries will also be provided for study intervention-related SAEs. The summary tables will be displayed by PT and SOC. A study intervention-related SAE is defined as an SAE for which the investigator classifies the relationship to study intervention as “Yes”. A worst-case scenario approach will be taken to handle missing data, i.e. the summary table will include events with the relationship to study intervention as ‘Yes’ or missing. Summaries and listings of adverse events will include treatment sequence. A listing of AEs that occur during Follow-up will be provided. AEs leading to permanent discontinuation of study intervention and study intervention related AEs leading to permanent discontinuation of study intervention will be listed.

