4.4.3.2. Laboratory Data

Laboratory evaluations including the analyses of Chemistry laboratory tests, Hematology laboratory tests, Urinalysis, and liver function tests will be based on GSK Core Data Standards. When collected throughout the treatment period, laboratory data will be summarized based on observed values by visit and treatment sequence, as well as change from baseline by visit and treatment sequence. For laboratory data collected only at screening and follow-up visits, no summary will be produced. A listing of all laboratory data and a listing of PCI laboratory data will be produced.

Laboratory data includes the following variables:

Assessments	Parameters		
Haematology	
 • Platelet Count • Hematocrit • Hgb 	RBC Indices: 
 • MCV • MCH • %Reticulocytes 	WBC count with Differential: 
 • Neutrophils • Lymphocytes • Monocytes • Eosinophils • Basophils
Clinical Chemistry	
 • BUN • Creatinine • Glucose • Potassium • Sodium • Calcium 	
 • Aspartate Aminotransferase (AST)/Serum Glutamic-Oxaloacetic Transaminase (SGOT) 	
 • Total and direct bilirubin
	
 • Alanine Aminotransferase (ALT)/ Serum Glutamic-Pyruvic Transaminase (SGPT) 	
 • Alkaline phosphatase 	
 • Total Protein

Assessments	Parameters
Routine Urinalysis	
 • Specific gravity • pH, glucose, protein, blood, ketones, bilirubin, urobilinogen, nitrite, leukocyte esterase by dipstick • Microscopic examination (if blood or protein is abnormal)
Other Laboratory Analyses	
 • Follicle-stimulating hormone and estradiol (as needed in women of non-childbearing potential only) • Urine human chorionic gonadotropin (hCG) pregnancy test (as needed for women of childbearing potential) • HIV antibody • Folate, high sensitivity C-reactive protein, Vitamin B12

Separate summary tables for haematology, and chemistry laboratory tests will be produced. Liver function laboratory tests will be included with chemistry lab tests. Summaries of other laboratory analyses collected only at screening will not be produced.

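### Vital signs and on-treatment liver chemistry are tabulated only by sequence and visit; add summaries by treatment received and, for vital signs, a within-participant difference

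*SAP*

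**What the plan says.** For vital signs, SAP 4.4.3.3 says "Vital signs data will be summarized based on observed values by treatment sequence and visit", with change from baseline grouped the same way. On the baseline it says "Change from baseline will be calculated using one baseline for both periods (Day 1"). For laboratory data collected during treatment, SAP 4.4.3.2 says "laboratory data will be summarized based on observed values by visit and treatment sequence", again with change from baseline. It adds: "For laboratory data collected only at screening and follow-up visits, no summary will be produced".

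In the protocol schedule (Section 2), full chemistry and hematology are taken only at Week -4 and at the Day 70 follow-up. The row "Liver chemistry monitoring" is marked at Day 15 and Day 43. On-treatment vital signs fall on Day 29, before the crossover, and on Day 57.

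Other parts of the SAP group differently. For exposure, "Duration will be summarized by treatment group" (SAP 4.4.1). Iron markers and erythropoiesis indices are also summarised by treatment group (SAP 4.3, Evaluable Population). For adverse events, "Summaries and listings of adverse events will include treatment sequence" (SAP 4.4.2), and no treatment column is stated.

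SAP 1.1 lists vital signs as a safety endpoint next to "Incidence and severity of adverse events and serious adverse events". SAP 1.2 gives four sequences with N=3 each.

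**The concern.** Sequence is a poor grouping for a safety display in this design. Every sequence contains both drugs, and the split between A and B, or between C and D, reflects only which iron isotope came first. Isotope order has no evident bearing on blood pressure or liver tests, yet it divides the participants into four small cells.

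Worsening of hypertension is an adverse event of special interest (SAP 4.4.2.1), and protocol Appendix 3 says the data so far cannot refute that risk. The crossover supplies one on-treatment vital-signs assessment per drug per participant. The stated tables neither pool these by drug nor take the difference within participant. A reader of the study report who wants to know whether blood pressure differed between the drugs would have to assemble the answer from separate cells or from listings.

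**Working it through.** **The plan's own figures.** Four sequences of 3 make 12, the minimum Evaluable number. The stated 90% power for the primary endpoint reproduces: a paired t-test with 11 degrees of freedom and noncentrality (11/10.7) × √12 = 3.56 gives 89.9%. The two-sided 0.05 level is taken from the planned 95% intervals and two-sided p-values. This figure is not in dispute.

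**Which drug each cell represents** (sequence table in SAP 1.2, visits from protocol Section 2):

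| Sequence | Day 15 liver tests, Day 29 vital signs | Day 43 liver tests, Day 57 vital signs |
|---|---|---|
| A, B | rhEPO | daprodustat |
| C, D | daprodustat | rhEPO |

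Sequence plus visit therefore identifies the drug, and treatment means can be pooled by hand.

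**What the cells do not give.** The daprodustat-minus-rhEPO difference in change from Day 1 is:

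- in A and B: (Day 57 − Day 1) − (Day 29 − Day 1) = Day 57 − Day 29
- in C and D: Day 29 − Day 57

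The common baseline cancels. If τ is the treatment effect and π the period effect, and there is no carryover, these differences have expectation τ + π and τ − π. The average of the two order means is τ.

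The variance of the difference is Var(Day 29) + Var(Day 57) − 2 Cov(Day 29, Day 57). The SDs of observed values give the first two terms. Adding the SDs of change gives each visit's covariance with Day 1. Nothing in the means and SDs gives the covariance between Day 29 and Day 57, so the paired SD has to be rebuilt from listings. In a cell of exactly three, the minimum, median and maximum are the three values, and a reader could try to match them across visits. That would be reconstructing individual data, not reading a summary.

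**Information per cell.** The 95% CI half-width for a mean, in SD units, is t(0.975, n−1)/√n:

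| Grouping | n | Half-width |
|---|---|---|
| One sequence | 3 | 4.303/√3 = 2.48 SD |
| Sequences pooled by treatment order | 6 | 1.05 SD |
| Pooled by treatment received | 12 | 2.201/√12 = 0.64 SD |

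The ratio of the first to the last is 3.9. The documents give no SD for blood pressure. With an assumed SD of 15 mmHg for change in systolic pressure, the half-widths are about ±37 mmHg (n=3) and ±9.5 mmHg (n=12). For SDs of 10 to 20 mmHg they are about ±25 to ±50 and ±6 to ±13.

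**Adverse events.** A sequence column alone cannot show which drug was being taken at onset. SAP 6.2.2 classifies events by period, which together with sequence identifies the drug, but SAP 4.4.2 does not say that its tables use that classification.

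**The case against.** The strongest reply is that little is lost, and most of it stands.

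- A reader might infer that the plan gives no view of daprodustat against rhEPO. The documents do not support that: the drug is identifiable in every cell, both visits share one baseline, and full listings and listings of values of potential clinical importance are planned.
- A reader might infer that all laboratory data are affected. They are not: Hgb, haematocrit, red cell number, MCV and the iron markers are already shown by treatment group under SAP 4.3, although on the Evaluable rather than the Safety Population.
- A reader might infer that adverse events are shown only by sequence. SAP 4.4.2 says its summaries will include sequence, which does not exclude treatment columns. Display detail is deferred to a separate programming specification that is not available here. The gap is an unstated column, not a sequence-only rule.
- The safety objective is to assess, not to compare, and protocol 5.4 justifies the own-control design by iron absorption. The plan therefore breaks no promise.
- SAP 4.1.1 plans n, mean, SD, median, minimum and maximum. No interval is planned for these tables, and the half-widths above are for a mean, not for a treatment difference.
- Moving sequence to listings only would have a cost. No washout is described at Day 29, so treatment at onset can misattribute early Period 2 events, and sequence tables retain the order information.

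None of this supplies a pooled or paired by-treatment table for vital signs, or a pooled one for liver chemistry.

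**Conclusion.** The point holds as a gap in descriptive safety displays. For vital signs and on-treatment liver chemistry, the only stated grouping is sequence by visit. No stated table pools the two drugs, and none gives the paired difference in vital signs, although the data for both are collected and other sections of the same SAP summarise by treatment group.

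In size, a sequence cell of 3 is about 3.9 times less precise than a by-treatment mean of 12 (2.48 against 0.64 SD). This assumes the planned 3 per sequence and complete data in both periods. The Safety Population may exceed 12, so cells may be somewhat larger. The mmHg figures rest on an assumed SD and are illustrative only. The primary analysis, its power and data collection are unaffected. This is an inexpensive improvement to the plan, not a defect that threatens its conclusions.

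**What to change.** - **SAP 4.4.3.2 and 4.4.3.3:** add summaries by treatment received, pooled over sequences. rhEPO is Period 1 of A and B plus Period 2 of C and D; daprodustat is Period 2 of A and B plus Period 1 of C and D.
- **SAP 4.4.3.3:** add the within-participant daprodustat-minus-rhEPO difference in vital signs from Day 29 and Day 57, keeping the Day 1 baseline.
- **Day 70:** show follow-up values separately. Period 2 in SAP 6.2.2 has no end date, so without a rule these values would be counted with the Period 2 drug.
- **SAP 4.4.2:** state that adverse events are presented by treatment at onset alongside sequence.
- **Sequence tables:** keep them as supportive displays.

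The cost is SAP wording and a few table shells. No new data are needed, and nothing now planned is removed.

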4.4.3.4. ECG

A listing of all ECG data and a listing of PCI ECG data will be produced.

4.5. Changes to Protocol Defined Analyses

The fixed sequence effect has been removed from the mixed model specified for the primary analysis in protocol amendment 3 (Dated: 14-JUL-2021) to better align with recommendations in the literature (Kenward and [Roger](#), 2009).

5. SAMPLE SIZE DETERMINATION

Sufficient participants will be enrolled such that at least 12 participants comprise the Evaluable Population. A sample size of 12 participants provides 90% power to detect a paired mean difference in fractional iron absorption of 11% between the two treatment groups under an assumed between-participant standard deviation (SD) of 10.7%. Note this is a conservative estimate of the SD of the paired differences as it is based on a parallel design study ([Young, 2009](#)). No sample size re-estimation will be performed.

6. SUPPORTING DOCUMENTATION

6.1. Appendix 1 Study Population Analyses

Unless otherwise specified, the study population analyses will be based on the “Safety” population, unless otherwise specified. Screen failures will be summarized or listed based on the “Screened” population. A summary of the number of participants in each of the participant level analysis set will be provided.

6.1.1. Participant Disposition

A summary of the number and percentage of participants who completed the study as well as those who prematurely withdrew from the study will be provided overall and by study period. Reasons for study withdrawal will be summarized overall and by study period. For those who have neither completed nor withdrawn, they will be categorized as on study intervention or in follow up.

A summary of study intervention status will be provided. This display will show the number and percentage of participants who have completed the scheduled study intervention, are ongoing with study intervention, or have discontinued study intervention prematurely, as well as primary reasons for discontinuation of study intervention.

A summary of the number of subjects in the “Enrolled” population by country and site ID will be provided

6.1.2. Demographic and Baseline Characteristics

The demographic characteristics including age, sex, ethnicity, height at screening and race will be summarized with descriptive statistics. In addition, the following age categories will be summarized: 18-64, 65-84 and ≥ 85 based on the Enrolled Analysis Set.

Listings of demographic characteristics and race will also be produced.

6.1.3. Protocol Deviations

Important protocol deviations will be summarized.

Protocol deviations will be tracked by the study team throughout the conduct of the study. These protocol deviations will be reviewed to identify those considered as important as follows:

- Data will be reviewed prior to freezing the database to ensure all important deviations (where possible without knowing the study intervention details) are captured and categorised in the protocol deviations dataset.

○ This dataset will be the basis for the summaries of important protocol deviations. In addition to the overall summary of important protocol deviations, separate summaries will be produced for important protocol deviations related to COVID-19, and important protocol deviations not related to COVID-19 respectively.

6.1.4. Prior and Concomitant Medications

Prior and concomitant medications will be coded using both the GSK Drug and WHO Drug dictionaries. However, the summary will be based on GSK Drug dictionary only. However, they will only be presented in the form of ICH Listing.

For classifying study phase for concomitant medication, use the following definition.

Study Phase	Definition
Prior	If medication end date is not missing and is before 28 days prior to screening visit
Concomitant	Any medication that is not a prior

Please refer to 6.2.6: for handling of missing and partial dates for concomitant medication. Use the rules in this table if concomitant medication date is completely missing.

6.1.5. Study Intervention Compliance

A summary of overall compliance for daprodustat based on the exposure data will be produced. Overall compliance will be summarized using descriptive statistics as well as the categories <80%, 80%-105%, and >105%.

Study intervention Compliance (%) = [Total cumulative actual dose / Total cumulative scheduled dose] * 100.

6.1.6. Additional Analyses Due to the COVID-19 Pandemic

A participant is defined as having a suspected, probable, or confirmed COVID-19 infection during the study if the answer is “Confirmed”, “Probable” or “Suspected” to the case diagnosis question from the COVID-19 coronavirus infection assessment eCRF. Numbers of participants with a suspected, probable, or confirmed COVID-19 infection, and of COVID-19 test results will be summarized.

6.2. Appendix 2 Data Derivations Rule

6.2.1. Criteria for Potential Clinical Importance

A laboratory value that is outside the reference range is considered either high abnormal (value above the upper limit of the reference range) or low abnormal (value below the lower limit of the reference range). Note: a high abnormal or low abnormal laboratory value is not necessarily of clinical concern.

In addition, the following criteria will be used to flag potential clinical importance (PCI) in the Safety population:

• Haematology				
Laboratory Parameter	Units	Category	Clinical Concern Range	
			Low Flag (< x)	High Flag (>x)
Hematocrit	Ratio of 1	Male	0.225	0.54
		Female	0.225	0.46
Hemoglobin	g/L	Male	75	175
		Female	75	153
Platelet Count	x10 ⁹ / L		<80	>500
RBC Count	x10 ¹² / L		<4	>5
WBC Count with Differential:			< LLRR	> 5x ULRR
Neutrophils	mm ³		< 0.5	N/A
Lymphocytes	mm ³		<0.5	N/A
Monocytes	mm ³		<0.2	>1.0
Eosinophils	mm ³		N/A	>0.5
Basophils	mm ³		N/A	>0.1
RBC Indices:				
MCV	Femtolitres/cell		<80	>96
MCH	picograms/cell		<27	>33
%Reticulocytes	%		<0.5	>1.5

Clinical Chemistry				
Laboratory Parameter	Units	Category	Clinical Concern Range	
			Low Flag (< x)	High Flag (>x)
Calcium	mmol/L		<1.75	>2.74
Creatinine	umol/L		<44.21	>884
Glucose	mmol/L		<3.9	>18
Total Protein	g/L		<60	>90
Potassium	mmol/L		<3.5	> 6.0

Clinical Chemistry				
Laboratory Parameter	Units	Category	Clinical Concern Range	
			Low Flag (< x)	High Flag (>x)
Sodium	mmol/L		< 130	> 150

Liver Function			
Test Analyte	Units	Category	Clinical Concern Range
ALT/SGPT	U/L	High	>= 3x ULRR
AST/SGOT	U/L	High	>= 3x ULRR
AlkPhos	U/L	High	>150
T Bilirubin	µmol/L	High	>= 2x ULRR
Direct Bilirubin	µmol/L	High	>8.0

Other Laboratory analyses				
Laboratory Parameter	Units	Category	Clinical Concern Range	
			Low Flag (< x)	High Flag (>x)
Ferritin	ng/ml		<100	>800
TSAT	%		<15	>40
Folate	ng/ml		<2.0	N/A
high sensitivity C-reactive protein	micrograms /ml		N/A	>/=20
Vitamin B12			</= LLRR at screening	N/A

ECG Parameter	Units	Clinical Concern Range	
		Lower	Upper
Absolute			
Heart rate	bpm	40	125
PR Interval	msec	80	230
QRS Duration	msec	50	130
RR	breaths/mit	8	25
Uncorrected QT Interval	msec	300	500
QTcF	msec	300	500
QTcB	msec	300	500
QTc (Unspecified)	msec	300	500
RR Interval	msec	545	1500

Vital Sign Parameter (Absolute)	Units	Clinical Concern Range	
		Lower	Upper
Systolic Blood Pressure	mmHg	85	170
Diastolic Blood Pressure	mmHg	50	110
Heart Rate	bpm	40	125
Change from baseline			
Systolic Blood Pressure	mmHg		>30
Diastolic Blood Pressure	mmHg		>50
Heart Rate	bpm		>30

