6.1. Inclusion Criteria

Participants are eligible to be included in the study only if all the following criteria apply:

Age

1. Participant must be at least 18 years of age inclusive, at the time of signing the informed consent.

Type of Participant and Disease Characteristics

2. Participants who are Stage 3, 4 or 5 CKD (confirmed at Week -4 only) defined by eGFR using the CKD Epidemiology Collaboration (CKD-EPI) formula ([Levey, 2009](#)). See the Study Reference Manual (SRM) for details on calculation.

3. Participants who are currently treated with stable doses ($\leq 50\%$ change in 4-weekly dose) for at least 8 weeks prior to and including the screening period, of rhEPO (i.e., epoetin alfa or darbepoetin alfa).
4. Participants with Hgb levels between 9.0 and 11.5 g/dL, inclusive, who meet the Hgb stability criteria as outlined in Section 6.2.1.
5. Participants may be on stable maintenance oral iron supplementation ($<50\%$ change in overall dose and compliance of 80% of prescribed doses in the 4 weeks prior to and including the screening period). If participants have been on IV iron, then participants will not have received IV iron for 8 weeks prior to the Day 1 visit.

Sex

6. Male or female

a. Female participants:

A female participant is eligible to participate if she is not pregnant (see [Appendix 7](#)), not breastfeeding, and at least one of the following conditions applies:

- (i) Not a woman of childbearing potential (WOCBP) as defined in [Appendix 7](#)

OR

- (ii) A WOCBP who agrees to follow the contraceptive guidance in [Appendix 7](#) during the treatment period to the follow-up visit.

Informed Consent

7. Capable of giving signed informed consent as described in [Appendix 5](#) which includes compliance with the requirements and restrictions listed in the informed consent form (ICF) and in this protocol.

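### Three sets of PCI criteria in SAP 6.2.1 (white-cell differential units, diastolic rise, RBC <4) do not discriminate as written

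*SAP*

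**What the plan says.** SAP 6.2.1 tabulates the PCI limits for the Safety population. The entries that matter here are:

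- **Blood pressure, change from baseline:** "Systolic Blood Pressure mmHg >30" and, in the "Diastolic Blood Pressure" row, "Diastolic Blood Pressure mmHg >50".
- **Blood pressure, absolute (lower and upper limit):** "Systolic Blood Pressure mmHg 85 170" and "Diastolic Blood Pressure mmHg 50 110".
- **Red cells:** RBC count below 4 or above 5 x10^12/L. The same table flags haemoglobin below 75 g/L, hematocrit below 0.225, MCV outside 80 to 96 fL and MCH outside 27 to 33 pg ("picograms/cell <27 >33").
- **Differentials, unit given as mm3:** neutrophils <0.5, lymphocytes <0.5, monocytes <0.2 or >1.0, eosinophils >0.5, basophils >0.1. The platelet row uses x10^9/L.

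The limits feed planned outputs. For vital signs, SAP 4.4.3.3 states: "A listing of all Vital signs data and a listing of PCI Vital signs data will be produced". SAP 4.4.3.2 plans the same pair of listings for laboratory data. Protocol 6.1 admits "Participants with Hgb levels between 9.0 and 11.5 g/dL, inclusive".

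**The concern.** A PCI limit is useful if it picks out the few values that deserve a second look. A limit that almost nobody or almost everybody meets does not do that, and a programmer coding the table literally would carry the fault into the safety outputs.

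The context gives this some weight. Vital signs are a named safety endpoint and worsening of hypertension is an adverse event of special interest, so a diastolic rise is something the PCI listing should be able to show. For differentials, the Schedule of Activities takes haematology only at Week -4 and Day 70, and SAP 4.4.3.2 produces no summary for laboratory data collected only at screening and follow-up. The PCI listing is therefore the only filtered view of those counts.

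**Working it through.** The plan states no derived figure to reproduce, so the check tests each limit against the plan's other figures.

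**1. Differentials.** Conversion: 1 x10^9/L = 1000 per mm3.

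- As written, 0.5 per mm3 = 0.0005 x10^9/L and 0.2 per mm3 = 0.0002 x10^9/L. The low neutrophil, lymphocyte and monocyte flags fire only at essentially zero cells.
- The high flags (monocytes >1.0, eosinophils >0.5, basophils >0.1 per mm3) fire on virtually any non-zero count.
- Read as x10^9/L, the same numbers become neutrophils and lymphocytes <500, monocytes <200 or >1000, eosinophils >500 and basophils >100 per mm3. These are on the scale of real counts, and the unit matches the platelet row.

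**2. Diastolic rise.** Inputs: change limit >50, absolute upper limit 110 (SAP 6.2.1).

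- 110 - 50 = 60. From a baseline of 60 mmHg or more, a rise above 50 ends above 110 and is already flagged. The change rule can add a flag only from a baseline below 60.
- A rise from 75 to 105 mmHg is +30 and ends below 110, so neither diastolic rule flags it.
- The order is reversed relative to the absolute limits: the upper limit is lower for diastolic (110) than for systolic (170), yet the change limit is higher (50 against 30).
- The documents give no SD for diastolic change. Assuming a normal change with mean 0, P(rise >50) = 1 - Phi(50/SD) per reading:

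| Assumed SD (mmHg) | P(rise >50) |
|---|---|
| 8 | 2e-10 |
| 10 | 3e-7 |
| 12 | 2e-5 |
| 15 | 0.0004 |
| 20 | 0.006 |

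**3. RBC <4.** Formula: RBC (10^12/L) = Hgb (g/L) / MCH (pg). Inputs: entry Hgb 90 to 115 g/L (Protocol 6.1) and the table's own unflagged MCH of 27 to 33 pg.

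- Lowest: 90/33 = 2.73. Highest: 115/27 = 4.26.
- RBC = 4 at MCH 27 needs Hgb 4 x 27 = 108 g/L. Below that, every value with MCH of at least 27 is flagged. At Hgb 115, a value is flagged whenever MCH exceeds 115/4 = 28.75.
- Share flagged, if Hgb and MCH are uniform over these ranges (an assumption): the unflagged triangle is 0.5 x (115 - 108) x (28.75 - 27) = 6.125 of a total 25 x 6 = 150, about 4%, so about 96% are flagged. With MCH assumed normal, mean 28 to 31 and SD 2, the share is 80 to 98%.
- If Hgb is uniform from 90 to 130 g/L instead: 0.5 x 22 x 5.5 = 60.5 of 40 x 6 = 240 is unflagged, so about 75% are flagged.

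Within the table, the Hgb flag of 75 g/L corresponds to RBC 75/33 = 2.27 to 75/27 = 2.78. The hematocrit flag of 0.225, at the unflagged MCV of 80 to 96 fL, corresponds to RBC 0.225/96 = 2.34 to 0.225/80 = 2.81 (x10^12/L after units). RBC <4 instead corresponds to Hgb below 4 x 27 = 108 to 4 x 33 = 132 g/L. Related measures of the same anaemia are thus flagged at very different depths.

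**The case against.** The best defence is that little depends on these cells, and most of that stands. Full listings of all laboratory and vital-sign data are planned, vital signs are summarised by sequence and visit without PCI limits (SAP 4.4.3.3), and RBC number is summarised as a secondary endpoint (SAP 4.3). Events of special interest are summarised from adverse events (SAP 4.4.2.1), and the stopping rules in Protocol 8.1.1 and 8.2.1 do not refer to PCI flags. In a study sized for 12 evaluable participants, a rise from 75 to 105 mmHg would be visible in the full listing.

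On red cells, the defence notes that frequent flags are expected in anaemia and that the SAP itself says an out-of-range value is not necessarily of clinical concern. It is also right that some participants escape. At MCH 25 and Hgb 10.0 g/dL, RBC is 100/25 = 4.0. Participants may continue with Hgb up to <13.0 g/dL (Protocol 8.2.1.1), and at Hgb 12.5 and MCH 30, RBC is 125/30 = 4.17. Neither is flagged, so the claim is about most participants, not all. This does not explain why the RBC limit sits so far from the Hgb and hematocrit limits beside it.

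On differentials, the unit is very probably a labelling slip that a programmer might notice. A multiplier may also have been lost when the table was converted to text; if the signed SAP carries one, this part falls away. As it reads, the unit is wrong, and noticing it should not be left to chance.

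**Conclusion.** The point holds as a minor correction. Two results rest only on the documents' own figures: the conflict between the diastolic change limit and the limits around it, and the RBC range of 2.73 to 4.26 at entry Hgb with MCH of 27 to 33 pg. The differential result is unit conversion together with the ordinary scale of cell counts. The shares flagged for RBC and the diastolic probabilities depend on assumed distributions and show scale only.

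A reader might go further and infer that the blood pressure and haematology PCI listings become useless, or that the vital-signs endpoint would miss real rises. The documents do not support this. Systolic change, absolute systolic and diastolic, Hgb, hematocrit, platelet and total white-cell criteria still work, and the endpoint's summaries and full listing use no PCI limit. Nor can it be said that the neutrophil flag could never fire: as written it would fire at essentially zero cells.

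**What to change.** In SAP 6.2.1, before the PCI listings are programmed:

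- Relabel the unit of the five differential rows as x10^9/L, leaving the numbers as they are.
- Reconcile the diastolic change limit with the systolic change limit and the absolute diastolic limits. The documents do not show which value was intended, so this needs clinical sign-off.
- Reconcile the RBC limit with the Hgb and hematocrit flags in the same table and with the entry Hgb range, also with clinical sign-off.

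The cost is a few cells in an appendix table. No data collection, sample size or primary or secondary analysis changes.
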